## **8.8 PUBLICATION POLICY**

Boehringer Ingelheim is as much as possible dedicated to support process of free exchange of relevant scientific information. Any publication of the result of this trial must be consistent with the Boehringer Ingelheim publication policy. The rights of the investigator and of the sponsor with regard to publication of the results of this trial are described in the investigator contract. As a general rule, no trial results should be published prior to finalisation of the Clinical Trial Report (CTR).

## **8.9 COMPLETION OF TRIAL**

The EC/competent authority in each participating EU member state needs to be notified about the end of the trial or early termination of the trial.

## 10. APPENDICES

### 10.1 HANDLING PROCEDURE OF BLOOD SAMPLES FOR PLASMA CONCENTRATION-TIME MEASUREMENTS

Table 10.1: 1 Time schedule for PK blood sampling

Treatment Period	Visit	Event Name	Day	Time Frame [hh:min]	CRF Time /PTM	Event	Sample No
During RT	2	V2	8	Just before BIBW intake	-0:05	PK Blood	1
	3	V3	15	Just before BIBW intake	-0:05	PK Blood	2
				0:30 – 2:00	1:00	PK Blood	3
				2:00 – 4:00	3:00	PK Blood	4
				4:00 – 24:00	6:00	PK Blood	5 voluntary
	4	V4	29	Just before BIBW intake	-0:05	PK Blood	6

### 10.2 HANDLING OF MISSING DATA

#### 10.2.1 Plasma concentration - time profiles

Concentration data identified with NOS (no sample available), NOR (no valid result), NOA (not analyzed), BLQ (below the limit of quantification), and NOP (no peak detectable) will be ignored and not replaced by zero at any time point (applies also to the lag phase including the pre-dose value). Descriptive statistics of concentrations at specific time points will be calculated only when at least 2/3 of the individuals have concentrations within the validated concentration range. The overall sample size to decide whether the “2/3 rule” is fulfilled will be based on the total number of samples intended to be drawn for that time point (i.e. BLQ, NOR, NOS, NOA, NOP are included).

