### **7.2 NULL AND ALTERNATIVE HYPOTHESES**

No formal hypothesis testing is planned.

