### **7.3.5 Pharmacokinetic methods**

BIBW 2992 plasma concentrations will be summarized by time point by descriptive statistics and, if feasible, graphically inspected. Predose (trough) plasma concentrations will be compared to historical data to estimate a possible effect of RT and/or TMZ on the pharmacokinetics of BIBW 2992.

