6.6 HANDLING OF MISSING DATA AND OUTLIERS

PK parameters:

Missing data and outliers of PK data are handled according to BI standards. (2)

Time from first histological diagnosis:

If day of first histological diagnosis is missing it will be imputed using 15.

If both day and month of first histological diagnosis is missing they will be imputed using 1st July.

Adverse events:

Missing or incomplete AE dates are imputed according to BI standards. (4)

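### Protocol Appendix 10.2.1 drops below-quantification troughs as if missing: if any occur, the trough summary compared with historical data is biased upward, and a large fall in exposure produces no statistic

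*Protocol*

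**What the plan says.** Protocol Appendix 10.2.1 lists five result codes: no sample (NOS), no valid result (NOR), not analysed (NOA), below the limit of quantification (BLQ) and no peak detectable (NOP). All five "will be ignored and not replaced by zero at any time point", and a parenthesis adds that this "applies also to the lag phase including the pre-dose value". Statistics at a time point are "calculated only when at least 2/3 of the individuals have concentrations within the validated concentration range". The denominator of that rule is "based on the total number of samples intended to be drawn for that time point", so BLQ and missing samples both count against the threshold.

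Protocol 7.3.5 gives the troughs their purpose: "Predose (trough) plasma concentrations will be compared to historical data to estimate a possible effect of RT and/or TMZ". Section 5.5.1 and Appendix 10.1 place every predose sample on Day 8, 15 or 29.

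On PK data the SAP says only this (section 6.6): "Missing data and outliers of PK data are handled according to BI standards". Its section 7.5.2 also defers the PK analysis to the sponsor's standard. Protocol 7.4.1 points to Appendix 10.3 for PK missing data, but that appendix is the Karnofsky scale; the rule is in 10.2.

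**The concern.** A BLQ result is not missing. It says that the concentration is below a known limit. Before a first dose that carries little information, and ignoring it does little harm. This trial takes no such sample: every predose sample falls on or after Day 8, and Protocol 1.2.1 says steady state is reached within 8 days. A BLQ trough here therefore means low exposure, whether from an interaction, a missed dose or something else.

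Dropping it removes the lowest values from the summary meant to show whether exposure has fallen. The bias grows as exposure falls, until more than a third of values are lost and the time point is no longer summarised. Neither Appendix 10.2.1 nor section 7.3.5 asks for BLQ counts, so a reader of the table could not tell a low result from a lost sample.

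**Working it through.** The plan states no trough mean, variability, quantification limit or BLQ rate, so it has no figure to reproduce. The variability and BLQ shares below are assumptions.

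**1. How many values can be dropped.** The two-thirds rule, with all intended samples as denominator, allows 1 of 3, 2 of 6 or 4 of 12 (3 is the initial cohort size; 6 and 12 are the sizes in Protocol 7.6). One more BLQ or missing value and no statistic is calculated.

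**2. Inflation from dropping the lowest share f.** Assume log-normal troughs with log-scale SD s. Let z be the standard normal f-quantile, φ the normal density and Φ its distribution function.

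- Geometric mean: exp(s·φ(z)/(1−f)) − 1
- Arithmetic mean: Φ(s−z)/(1−f) − 1

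| f | z | φ(z)/(1−f) | Geometric mean, s = 0.4 / 0.6 / 0.8 | Arithmetic mean, s = 0.4 / 0.6 / 0.8 |
|---|---|---|---|---|
| 10% | −1.282 | 0.195 | 8% / 12% / 17% | 6% / 8% / 9% |
| 20% | −0.842 | 0.350 | 15% / 23% / 32% | 12% / 16% / 19% |
| 1/3 (cap) | −0.431 | 0.545 | 24% / 39% / 55% | 20% / 27% / 34% |

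Example at the cap with s = 0.8: the geometric mean gives exp(0.8 × 0.545) = 1.55. The arithmetic mean gives Φ(1.231)/(2/3) = 0.891/0.667 = 1.34.

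**3. Small cohorts.** Simulated order statistics with coefficient of variation (CV) 30% to 90%, where s = √ln(1+CV²), give geometric-mean inflation of 13% to 39% for 1 of 3 dropped, 15% to 45% for 2 of 6, and 16% to 48% for 4 of 12.

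**4. Effect on an apparent fall.** As an example size only, take a true fall of 34% (ratio 0.66), the AUC change that Protocol 1.2.1 reports with rifampicin. If a share q0 of historical troughs is BLQ, with quantile z0, the trial quantile is z1 = z0 − ln(0.66)/s and the trial BLQ share is q1 = Φ(z1). Write h(z) = φ(z)/(1−Φ(z)). The apparent ratio of geometric means is 0.66·exp(s·[h(z1) − h(z0)]) if the same rule was used historically, and 0.66·exp(s·h(z1)) if the historical figure carries no dropping bias.

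With q0 = 5% and CV 50%: s = 0.472, z1 = −1.645 + 0.880 = −0.765, q1 = 22%, h(z0) = 0.109 and h(z1) = 0.383. The same-rule ratio is 0.66 × exp(0.472 × 0.274) = 0.751.

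| CV (q0 = 5%) | Trial BLQ share | Apparent fall, same rule | Apparent fall, unbiased historical data |
|---|---|---|---|
| 30% | 41% | suppressed | suppressed |
| 50% | 22% | 25% | 21% |
| 90% | 13% | 26% | 20% |

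If historical BLQ is only 1%, the same-rule fall appears as 28% to 31% (CV 30% to 90%); at 0.1% it appears as 32% to 33%.

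**5. Are BLQ troughs likely?** Protocol 1.2.1 gives a half-life mainly of 13 to 57 h and a median tmax of 1 to 6 h. Under mono-exponential decline over a 24 h interval, trough/peak = exp(−ln2·(24−tmax)/t½). This runs from 0.29 (13 h, tmax 1 h) to 0.80 (57 h, tmax 6 h), so BLQ troughs may be few. Without the quantification limit this cannot be settled.

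**The case against.** A reader might infer that the trough averages in this trial will be taken from the higher values only and that a fall in exposure is understated. The documents do not support that as fact. It happens only if troughs are BLQ, and step 5 suggests they may be rare under once-daily dosing at steady state.

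Other points on that side:

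- The two-thirds rule caps the bias and withholds the mean beyond the cap, so a grossly inflated mean is never printed. This stands, but withholding is no cure: the time point with the strongest signal gets no number.
- The SAP's default statistics (section 7) are N, mean, SD, minimum, median and maximum. The smaller arithmetic-mean figures are therefore the safer ones to cite, unless the sponsor's PK standard adds a geometric mean. A reader would also see N fall and, where feasible, a plot. N does not show whether the loss was a low value or a lost sample.
- If the historical data were handled the same way, part of the bias cancels. This stands, but step 4 shows that some remains when BLQ is more frequent in the trial. The historical rule is not stated.
- Half-limit substitution would not be a clean cure. It gives about 0.85 to 0.97 of the true geometric mean at 10% to 33% BLQ (CV 30% to 90%), and applying it to this trial alone could create an apparent fall. This stands, and the fix does not require it.
- The sponsor's standard may already ask for BLQ counts. It cannot be seen from these documents, while the protocol's explicit rule can.
- PK is a secondary endpoint (Protocol 2.3), the comparison is descriptive, and "No formal hypothesis testing is planned". This stands and limits the weight of the point.

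**Conclusion.** The concern holds as a conditional one. If any steady-state trough is BLQ or NOP, the rule biases upward the summary that section 7.3.5 compares with historical data; if more than a third of intended samples are lost, it reports nothing. On the step 2 assumptions, the inflation runs from about 6-9% (arithmetic mean) or 8-17% (geometric mean) with 10% dropped, to about 20-34% or 24-55% at the cap.

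These figures rest on log-normal troughs, an assumed log-scale SD of 0.4 to 0.8, and BLQ values that really are low concentrations. The net bias in the comparison cannot be fixed from the documents and is zero if no trough is BLQ. It is also wrong to conclude that a fall would generally be hidden: in the example a 34% fall is attenuated or left unsummarised, and barely changed when BLQ is rare. MTD determination rests on DLTs and is unaffected. The change is worth making because it is nearly free.

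**What to change.** In Appendix 10.2.1 and the SAP, for the trough comparison:

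- Treat only NOS, NOR and NOA as missing.
- At each predose time point, print the number of BLQ/NOP results and the quantification limit.
- Report a median that ranks BLQ/NOP results below the limit, shown as '<LLOQ' if it falls there, instead of suppressing the time point. This needs no imputed value.
- Keep the existing quantifiable-only summary beside it for comparability.
- State the BLQ rule used for the historical data, and apply one rule to both sides where possible.
- Optionally add a censored log-normal estimate as a sensitivity analysis where cohort size allows; it will be fragile in cohorts of 3 to 6. Do not make half-limit substitution mandatory.

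Correct the cross-reference in Protocol 7.4.1 to Appendix 10.2 at the same time.

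Cost: a short text change and one extra row or column in the PK tables. No new samples or patients are needed.

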### 10.3 KARNOFSKY PERFORMANCE SCALE

Able to carry on normal activity and to work; no special care needed.	100	Normal no complaints; no evidence of disease.
	90	Able to carry on normal activity; minor signs or symptoms of disease.
	80	Normal activity with effort; some signs or symptoms of disease.
Unable to work; able to live at home and care for most personal needs; varying amount of assistance needed.	70	Cares for self; unable to carry on normal activity or to do active work.
	60	Requires occasional assistance, but is able to care for most of his personal needs.
	50	Requires considerable assistance and frequent medical care.
Unable to care for self; requires equivalent of institutional or hospital care; disease may be progressing rapidly.	40	Disabled; requires special care and assistance.
	30	Severely disabled; hospital admission is indicated although death not imminent.
	20	Very sick; hospital admission necessary; active supportive treatment necessary.
	10	Moribund; fatal processes progressing rapidly.
	0	Dead

### 10.4 MINI MENTAL STATE EXAMINATION (MMSE)

Date of Examination \_\_\_\_\_/\_\_\_\_\_/\_\_\_\_\_ Examiner \_\_\_\_\_  
 Name \_\_\_\_\_ Age \_\_\_\_\_ Years of School Completed \_\_\_\_\_

**Instructions:** Words in boldface type should be read aloud clearly and slowly to the examinee. Item substitutions appear in parentheses. Administration should be conducted privately and in the examinee's primary language. Circle 0 if the response is incorrect, or 1 if the response is correct. Begin by asking the following two questions:

**Do you have any trouble with your memory?      May I ask you some questions about your memory?**

ORIENTATION TO TIME	RESPONSE	SCORE (circle one)
What is the... year?	_____	0   1
season?	_____	0   1
month of the year?	_____	0   1
day of the week?	_____	0   1
date?	_____	0   1

ORIENTATION TO PLACE*	RESPONSE	SCORE (circle one)
Where are we now? What is the... state (province)?	_____	0   1
county (or city/town)?	_____	0   1
city/town (or part of city/neighborhood)?	_____	0   1
building (name or type)?	_____	0   1
floor of the building (room number or address)?	_____	0   1

\*Alternative place words that are appropriate for the setting and increasingly precise may be substituted and noted.

**REGISTRATION\***

Listen carefully. I am going to say three words. You say them back after I stop. Ready? Here they are... **APPLE** [pause], **PENNY** [pause], **TABLE** [pause]. Now repeat those words back to me. [Repeat up to 5 times, but score only the first trial.]

APPLE	_____	0   1
PENNY	_____	0   1
TABLE	_____	0   1

Now keep those words in mind. I am going to ask you to say them again in a few minutes.

\*Alternative word sets (e.g., PONY, QUARTER, ORANGE) may be substituted and noted when retesting an examinee.

**ATTENTION AND CALCULATION [Serial 7s]\***

Now I'd like you to subtract 7 from 100. Then keep subtracting 7 from each answer until I tell you to stop.

What is 100 take away 7?	[93]	_____	0   1
If needed, say: Keep going.	[86]	_____	0   1
If needed, say: Keep going.	[79]	_____	0   1
If needed, say: Keep going.	[72]	_____	0   1
If needed, say: Keep going.	[65]	_____	0   1

\*Alternative item (WORLD backward) should only be administered if the examinee refuses to perform the Serial 7s task. →

Reproduced by special permission of the publisher, Psychological Assessment Resources, Inc., [name], from the Mini Mental State Examination, by Marshall Folstein and Susan Folstein, Copyright 1975, 1998, 2001 by Mini Mental LLC, Inc. Published 2001 by Psychological Assessment Resources, Inc. Further reproduction is prohibited without permission of PAR, Inc. The MMSE can be purchased from PAR, Inc by calling [contact].

Substitute and score this item only if the examinee refuses to perform the Serial 7s task.

**Spell WORLD forward, then backward.**

Correct forward spelling if misspelled,  
 but score only the backward spelling.

(D = 1) (L = 1) (R = 1) (O = 1) (W = 1) (0 to 5)

**RECALL**

**RESPONSE**

**SCORE**  
 (circle one)

What were those three words I asked you to remember? [Do not offer any hints.]

APPLE	_____	0	1
PENNY	_____	0	1
TABLE	_____	0	1

**NAMING\***

What is this? [Point to a pencil or pen.]

\_\_\_\_\_ 0 1

What is this? [Point to a watch.]

\_\_\_\_\_ 0 1

\*Alternative common objects (e.g., eyeglasses, chair, keys) may be substituted and noted.

**REPETITION**

Now I am going to ask you to repeat what I say. Ready? "NO IFS, ANDS, OR BUTS." Now you say that.

[Repeat up to 5 times, but score only the first trial.]

NO IFS, ANDS, OR BUTS. \_\_\_\_\_ 0 1

Detach the next page along the lengthwise perforation, and then tear it in half along the horizontal perforation. Use the upper half of the page (blank) for the Comprehension, Writing, and Drawing items that follow. Use the lower half of the page as a stimulus form for the Reading ("CLOSE YOUR EYES") and Drawing (intersecting pentagons) items.

**COMPREHENSION**

Listen carefully because I am going to ask you to do something.

Take this paper in your right hand [pause], fold it in half [pause], and put it on the floor (or table).

TAKE IN RIGHT HAND	_____	0	1
FOLD IN HALF	_____	0	1
PUT ON FLOOR (or TABLE)	_____	0	1

**READING**

Please read this and do what it says. [Show examinee the words on the stimulus form.]

CLOSE YOUR EYES \_\_\_\_\_ 0 1

**WRITING**

Please write a sentence. [If examinee does not respond, say: Write about the weather.]

0 1

Place the blank piece of paper (unfolded) in front of the examinee and provide a pen or pencil. Score 1 point if the sentence is comprehensible and contains a subject and a verb. Ignore errors in grammar or spelling.

**DRAWING**

Please copy this design. [Display the intersecting pentagons on the stimulus form.]

0 1

Score 1 point if the drawing consists of two 5-sided figures that intersect to form a 4-sided figure.

[figure not shown]
Assessment of level of consciousness.

Total Score = _____
(Sum all item scores.) (30 points max.)

Alert/ Responsive	Drrowsy	Stuporous	Comatose/ Unresponsive
----------------------	---------	-----------	---------------------------

**CLOSE YOUR EYES**

Sample Only  
Copyright Protected

## 10.5 COCKCROFT-GAULT-FORMULA

The Cockcroft-Gault-Formula is commonly used to estimate GFR and is the recommended formula to calculate GFR in this trial.

$$\text{GFR} = \frac{(140 - \text{age}) \times \text{weight} \times F_S}{\text{serum creatinine} \times 72}$$

*Units: GFR [ml/min], age [years], weight [kg], serum creatinine [mg/dl],  $F_S$  is a correction Factor for Sex: in males  $F_S = 1$ , in females  $F_S = 0,85$*

## 10.6 RADIOTHERAPY TECHNIQUE

Patients should be treated with localised irradiation to the planning target volume (PTV) including the tumour [gross tumour volume (GTV), clinical target volume (CTV)] and a defined margin. Dose prescription and planning should follow the ICRU 50 guidelines.

### Immobilisation and imaging

All patients should be immobilised in an individually moulded immobilisation device (usually TP shell) specific to the department in a stable position (usually but not exclusively supine).

### Target volumes

The target volume is to be defined on post-operative planning CT/MRI together with pre-operative images. For enhancing tumours, the CTV is defined as the region of enhancement using the combination of the two sets of images. The PTV will be defined as the CTV with a margin of between 2 and 5cm, based on local practice although it is recommended that a standard 3cm margin is used around the CTV. For unenhancing tumours, the CTV should comprise the region of low intensity on T1 and high signal intensity on T2 and FLAIR sequences (low attenuation on CT). The PTV is defined as the CTV with a margin of 2 to 4 cm although it is recommended 2cm is used. For patients with a presumed transformed glioma which has both enhancing and unenhancing components, the CTV should be as for unenhancing tumours, including the full extent of the disease. In patients who have had complete macroscopic resection of the tumour, the CTV should be estimated from preoperative CT/MRI appropriately adjusted for a recognized shift due to resolution of a mass effect. In practice the CTV should at least cover the full excision cavity margins (not necessarily margins which would have been away from the primary tumour). The CTV – PTV margin should be as specified for unenhancing and enhancing tumours. In all instances the PTV should be adjusted/reduced when traversed by anatomical barriers to tumour migration and spread, such as the skull, falx or tentorium. This should therefore lead to outlining of volume to avoid extension into the orbit and below the cranial cavity beyond that necessary to account for immobilization and machine uncertainties. It is recommended that the same volume is used throughout the course of treatment

## **Planning and delivery**

Radiotherapy should be given conformally, using a multiple field technique and appropriate shielding or beam shaping to achieve PTV dose homogeneity as defined in ICRU 50. All fields should be treated daily. QA checks of delivery with on treatment imaging should be carried out according to local practice.

## **Dose limits**

The planning priority is to treat CTV and a minimum of 1cm margin to the prescribed dose. It is suggested that dose to critical structures such as the brain stem and the optic apparatus is kept below 55Gy although this should not be at the expense of CTV coverage. Peripheral portion of PTV may be adjusted to achieve normal tissue sparing. Scalp sparing techniques to avoid permanent hair loss should be used as is standard practice in the department but they must not compromise on a minimum 1cm CTV-PTV margin.

## **Radiotherapy schedule**

Radiotherapy should be given as fractionated treatment, delivering a total dose of 60 Gy in 6 weeks specified at 100%, given as a once daily schedule of 2 Gy per fraction, for a total of 30 fractions. All fields should be treated daily.

## **Delays in Radiotherapy**

Delays should be avoided if at all possible. There is a potential risk of bleeding in patients with low platelets, and if a platelet count  $< 25 \times 10^9/l$  is recorded, radiotherapy should be delayed until the platelets have recovered to  $> 50 \times 10^9/l$ .

## **Medical management during radiotherapy**

Corticosteroids should not be prescribed routinely for patients during radiotherapy. However in patients with raised intracranial pressure and/or progressive neurological deficit responsive to steroids, they can be prescribed at the discretion of the clinical team. The aim should be to titrate the dose to the lowest necessary to control the problems.

**10.7 LIST OF POTENT INHIBITORS AND INDUCERS OF P-GLYCOPROTEIN (MDR1)**

Inhibitors	Inducers
Amiodarone	Carbamazepine
Azithromycin	Phenytoin
Captopril	Rifampicin
Carvedilol	St John's Wort
Clarithromycin	Phenobarbital Salt
Conivaptan	Tipranavir
Cyclosporine	Ritonavir
Diltiazem	
Dronedarone	
Erythromycin	
Felodipine	
Itraconazole	
Ketoconazole	
Lopinavir	
Nelfinavir	
Ritonavir	
Quinidine	
Ranolazine	
Saquinavir	
Tacrolimus	
Ticagrelor	
Verapamil	

As the information on potent inhibitors and inducers of P-glycoprotein may evolve, it is important for the investigator to assess such status on concomitant therapies and in case of questions contact BI clinical monitor.

## **10.8 CLINICAL EVALUATION OF LIVER INJURY**

### **10.8.1 Introduction**

Alterations of liver parameters, as described in section 5.2.2.1 (Protocol-Specified Significant Events), are to be further evaluated using the following procedures:

### **10.8.2 Procedures**

Any elevation of ALT/AST and bilirubin qualifying as laboratory alert should be confirmed using the initial sample if possible.

If the alert is confirmed on initial sample, or it is not possible to repeat testing using initial sample, the following must be completed;

- 1) Evaluate the patient within 48 hours and,
- 2) Perform the following laboratory tests:
  1. Repeat of AST, ALT, bilirubin (with fractionation to total and direct)
  2. Haptoglobin
  3. Complete blood count and cell morphology
  4. Reticulocyte count
  5. Creatinine Kinase (CK)
  6. Lactate dehydrogenase (LDH)
  7. Alkaline Phosphatase

The results of these laboratory tests must be reported to BI as soon as possible.

If the initial alert values (i.e. AST,ALT, and bilirubin) are confirmed on the second sample described as above, then an abdominal ultrasound or clinically appropriate alternate imaging (to rule out biliary tract, pancreatic or intrahepatic pathology, e.g. bile duct stones or neoplasm) must be completed within 48 hours

The findings from the hepatic imaging (including comparison to prior imaging if available) must be made available as soon as possible as part of the adverse event reporting process. In the event the etiology of the abnormal liver tests results is not identified based on the imaging (e.g. biliary tract, pancreatic or intrahepatic pathology), then the “DILI checklist” must be completed. Details of the “DILI checklist” are provided in the ISF. The following assessments need to be performed in order to complete the “DILI checklist” and results will be reported via the eCRF:

- obtain a detailed history of current symptoms and concurrent diagnoses and medical history according to the “DILI checklist” provided in the ISF;
- obtain history of concomitant drug use (including non-prescription medications, herbal and dietary supplement preparations), alcohol use, recreational drug use, and special diets according to the “DILI checklist” provided in the ISF;

- obtain a history of exposure to environmental chemical agents (consider home and work place exposure) according to the “DILI checklist” provided in the ISF;
  - complete the following laboratory tests as detailed in the DILI checklist provided in the ISF:
    - *Clinical chemistry*  
alkaline phosphatase, cholinesterase (serum)\*, albumin, PT or INR, CK, CK-MB, coeruloplasmin\*,  $\alpha$ -1 antitrypsin\*, transferrin\*, amylase, lipase, fasting glucose, cholesterol, triglycerides
    - *Serology*  
Hepatitis A (Anti-IgM, Anti-IgG), Hepatitis B (HbsAg, Anti-HBs, DNA), Hepatitis C (Anti-HCV, RNA if Anti-HCV positive), Hepatitis D (Anti-IgM, Anti-IgG), Hepatitis E (Anti-HEV, Anti-HEV IgM, RNA if Anti-HEV IgM positive), Anti-Smooth Muscle antibody (titre), Anti-nuclear antibody (titre), Anti-LKM (liver-kidney microsomes) antibody, Anti-mitochondrial antibody, Epstein Barr Virus (VCA IgG, VCA IgM), cytomegalovirus (IgG, IgM), herpes simplex virus (IgG, IgM)\*, varicella (IgG, IgM)\*, parvovirus (IgG, IgM)\*
    - *Hormones, tumor-marker*  
Thyroid-stimulating hormone(TSH)\*
    - *Haematology*  
Thrombocytes, eosinophils
- \*If clinically indicated (e.g. immunocompromised patients)*
- **Long term follow-up**
- Initiate close observation of subjects by repeat testing of ALT, AST, and bilirubin (with fractionation to total and direct) at least weekly until the laboratory ALT and or AST abnormalities stabilize or return to normal, then according to the protocol. Depending on further laboratory changes, additional parameters identified e.g. by reflex testing will be followed up based on medical judgement and Good Clinical Practices (GCP).

and report these via the eCRF (for data not provided by a central laboratory).
